## 8.6 TRIAL MILESTONES

The **start of the trial** is defined as the date of the enrolment of the first patient in the whole trial ("First Patient In").

The **end of the trial** is defined as the date of the last visit (Visit 6/End of study Visit, please refer to [Section 6.2.3](#)) of the last patient in the whole trial ("Last Patient Out").

**Early termination of the trial** is defined as the premature termination of the trial due to any reason before the end of the trial as specified in this protocol.

**Temporary halt of the trial** is defined as any unplanned interruption of the trial by the Sponsor with the intention to resume it.

**Suspension of the trial** is defined as an interruption of the trial based on a Health Authority request.

The IEC / competent authority in each participating EU member state will be notified about the trial milestones according to the respective laws.

A final report of the clinical trial data will be written only after all patients have completed the trial in all countries (EU or non-EU) to incorporate and consider all data in the report.

The Sponsor will submit to the EU database a summary of the final trial results within one year from the end of a clinical trial as a whole, regardless of the country of the last patient (EU or non-EU).

## 10. APPENDICES

### 10.1 PHARMACOKINETIC ANALYSES

Pharmacokinetic evaluations will be performed according to the relevant Corporate Procedure of the Sponsor (001-MCS-36-472, current version).

Concentration data identified with NOS (no sample), NOR (no valid result), NOA (not analyzed), and BLQ (below the limit of quantification), will be ignored and not replaced by zero at any time point (applies also to the lag phase including the predose value). Descriptive statistics of concentrations at specific time points will be calculated only when at least 2/3 of the individuals have concentrations within the validated concentration range. The overall sample size to decide whether the “2/3 rule” is fulfilled will be based on the total number of samples intended to be drawn for that time point (i.e. BLQ, NOR, NOS, and NOA are included).

### 10.2 TIME AND VISIT SCHEDULE FOR PK, SAFETY AND BIOMARKER BLOOD SAMPLING

[figure not shown]
Table 10.2: 1 Time schedule for PK, Safety laboratory including [REDACTED] Biomarker and PGx blood sampling

Visit	Day	Sampling Time Point [hh:min]	CRF Time /PTM	PK	Safety	[REDACTED]	Biomarker sample	PGx
1	-28 to -2				X			
2a	1	Fasting blood collection:  Prior to drug administration  , between 08:30 a.m. and 10:30 a.m. (±30 min)	- 1:00	X	X	■	X	X
		0:00	0:00	First Drug administration				
3	29 (±3)	Prior to drug administration  , between 08:30 a.m. and 10:30 a.m. (±30 min)	- 1:00	X 	X			
		0:00	0:00	Drug administration				
		0:45 ± 15 min	0:45	X				
		2:30 ± 30 min	2:30	X				
		3:30 ± 30 min	3:30	X				

 Only at Day 1 (Visit 2a) blood collection will be in fasting state.

 Drug administration is planned to occur between 07:00 and 11:00 a.m., if possible.

 If possible, this sample is to be taken 12 hours ± 60 min after the evening drug intake on the previous day.

## 11. DESCRIPTION OF GLOBAL AMENDMENT(S)

Number of global amendment		1
Date of CTP revision		04 Mar 2016
EudraCT number		2015-003529-33
BI Trial number		1320.22
BI Investigational Product(s)		BI 1026706
Title of protocol		A randomized, double-masked, placebo-controlled exploratory study to evaluate pharmacodynamics, safety and tolerability of orally administered BI 1026706 for 12 weeks in patients with mild visual impairment due to center-involved diabetic macular edema (DME)
To be implemented only after approval of the IRB / IEC / Competent Authorities		
To be implemented immediately in order to eliminate hazard – IRB / IEC / Competent Authority to be notified of change with request for approval		
Can be implemented without IRB / IEC / Competent Authority approval as changes involve logistical or administrative aspects only		
Section to be changed		Section 3.3.3
Description of change		
Change 1: Section 3.3.3, Exclusion criteria  Added:            27. Male patients who do not agree to minimize the risk of female partners becoming pregnant from the first dosing day until 3 months after the trial medication treatment has finished 
 
Numbers of subsequent exclusion criteria changed accordingly.
 
Change 2: Footnote 1 of Exclusion criteria  Added:   Male patients who have sexual intercourse with women of childbearing potential will be instructed and must agree to use at least one of the following

[figure not shown]

		acceptable forms of effective contraception: - Established use of oral, injected or implanted hormonal methods of contraception by the female partner of the male patient - Placement of an intrauterine device (IUD) or intrauterine system (IUS) by the female partner of the male patient - Use of barrier methods of contraception: Condom or Occlusive cap (diaphragm or cervical/vault caps) with spermicidal foam/gel/film/cream/suppository - Sterilization of the male patient (with the appropriate post-vasectomy documentation of the absence of sperm in the ejaculate).
Rationale for change		Change 1: Section 3.3.3, Exclusion criterion 27. Specification, to align with Subject Information  Change 2: Footnote 1 of Exclusion criteria Specification, to align with Subject Information

2. LIST OF ABBREVIATIONS

Term	Definition / description
AE	Adverse event
██████	██
BRPM	Blinded report planning meeting
CSFT	Central Subfield Thickness
CTC	Common Terminology Criteria
CTP	Clinical Trial Protocol
CTR	Clinical Trial Report
CTX	Carboxy-Terminal Collagen Crosslinks
DM&SM	Boehringer Ingelheim Data Management and Statistics Manual
DRA	Drug Regulatory Affairs
DMG	Dictionary Maintenance Group
DME	Diabetic Macular Edema
EMEA	European Agency for the Evaluation of Medicinal Products
FAS	Full analysis set
HMA	Hemorrhage/ Micro-aneurysms
ICH	International Conference on Harmonisation
LOCF	Last observation carried forward
MedDRA	Medical Dictionary for Regulatory Activities
MMRM	Mixed-effect model for Repeated Measures
MQRM	Medical Quality Review Meeting
O*C	Oracle Clinical
██████	██
PK	Pharmacokinetics
PPS	Per protocol set
PSTAT	Project Statistician
PT	Preferred term
PV	Protocol violation
Q1	Lower quartile
Q3	Upper quartile
SA	Statistical analysis

[figure not shown]
Term	Definition / description
SD	Standard deviation
SD-OCT	Spectral-Domain Optical Coherence Tomography
SMQ	Standardised MedDRA query
SOC	System organ class
TCM	Trial Clinical Monitor
TESS	Treatment emergent signs and symptoms
ToC	Table of contents
TMW	Trial Medical Writer
TSAP	Trial statistical analysis plan

3. INTRODUCTION

As per ICH E9 [3], the purpose of this document is to provide a more technical and detailed elaboration of the principal features of the analysis described in the protocol, and to include detailed procedures for executing the statistical analysis of the primary and secondary variables and other data.

This TSAP assumes familiarity with the Clinical Trial Protocol (CTP), including Protocol Amendments. In particular, the TSAP is based on the planned analysis specification as written in CTP Section 7 “Statistical Methods and Determination of Sample Size”. Therefore, TSAP readers may consult the CTP for more background information on the study, e.g., on study objectives, study design and population, treatments, definition of measurements and variables, planning of sample size, randomization.

SAS[®] Version 9.4 or newer version will be used for all analyses.

5. ENDPOINTS

[figure not shown]
5.1 PRIMARY ENDPOINT

[figure not shown]
[figure not shown]
The primary endpoint will be the change from baseline in CSFT in μm at Week 12, as measured by SD-OCT. Baseline CSFT is determined at visit 2a. If not measured at Visit 2a, then baseline will be the value at Visit 1.

5.2 SECONDARY ENDPOINTS

Safety and tolerability of BI 1026706 will be assessed by the frequency of adverse events over the treatment period. The definitions of adverse events can be found in the protocol section 5.3.6.1

- Serious Adverse Events (SAEs)
- Drug related adverse events
- Adverse events of special interest (AESIs)

6. GENERAL ANALYSIS DEFINITIONS

6.1 TREATMENTS

For reporting purposes, all randomised patients will be classified into one of the following randomised treatment groups

Sort order	Treatment	Long label	Short label
01	C	BI 1026706 100mg film coated tablets	BI 1026706 100mg
02	D	Placebo matching BI 1026706 100mg film coated tablets	Placebo

These will be the default labels and sort order for reporting the treatment groups.

Patients will be analysed according to the treatment groups to which they were randomised. If there are cases of patients receiving incorrect treatment then an 'as treated' analysis will be performed in addition.

The following treatment periods based on actual start and stop dates of study treatment administration are defined:

Screening: day of informed consent to day prior to the start of randomised study medication

On-treatment: day of first administration of randomised study medication to the last day of study medication administration

Post-treatment: day after the last dose of randomised study medication and thereafter

For the safety analysis, post-treatment events that start up to 4 days after the last administration of trial medication will be assigned to randomised treatment. Adverse events that start on the 5th day after the last administration of trial medication will be considered post-treatment.

6.2 IMPORTANT PROTOCOL VIOLATIONS

The following table defines the different categories of important PVs. The final column describes which PVs will be used to exclude patients from the different patient analysis sets.

No per protocol (PPS) analysis will be performed for this study; however patients with important protocol violations (IPVs) will be documented. The following list of potential IPVs will be used; note this is a working list and may not be finalised until the final Blinded report planning meeting (BRPM) prior to database lock.

Table 6.2: 1 Important protocol violations

Category / Code	Description	Requirements	Excluded from
A	Entrance criteria not met		
A1.1	Inclusion criteria 1, 2, or 7 not met	Inclusion criteria 1, 2, or 7 not met as specified in the protocol.	None
A1.2	Trial diagnosis not met	Inclusion criteria 3, 4, 5, or 6 not met as specified in the protocol.	None
A2	Exclusion criteria present	Exclusion criteria as specified in the protocol present. Applies for criteria 1, 2, 5, 7, 9 – 23, 25-29	None
B	Informed consent		
B1	Informed consent not available/not done	Informed consent date missing; no signature on ICF	All
B2	Informed consent too late	Informed consent date was after Visit 1 date	None
C	Trial medication and randomization		
C1	Incorrect trial medication taken	Medication kit assigned not matching treatment patient was randomised to and/or not matching IVRS assignment	None

Table 6.2: 1 (continued) Important protocol violations

Category / Code	Description	Example/Comment	Excluded from
C2	Randomisation order not followed	Patient received trial medication from medication kit assigned to another patient	None
C3.1	Wrong dosage schedule	Capsules (BI 1026706 or matching placebo) taken once daily instead of bid and/or incorrect daily dose taken (more or less than two capsules)	None
C3.2	Treatment non-compliance	Overall compliance <80% or >120%. Final decision to be made at BRPM.	None
C4	Medication code broken inappropriately	Medication code broken inappropriately - reason for medication code break <reason> (Manual PV)	None
D	Concomitant medication		
D2	Prohibited medication taken concomitantly with study drug after randomization until End-of-Treatment visit is completed	
 • Systemic anti-VEGF or pro-VEGF treatment • Use of systemic steroids >10mg prednisone equivalent/day • Current or planned during the study period, use of medications known to be toxic to the retina, lens or optic nerve • plans to initiate intensive insulin treatment within the study period (Manual PV) • Potent and moderate CYP3A4 inhibitors • Potent and moderate CYP3A4 inducers • Potent and moderate P-gp inhibitors • Potent and moderate P-gp inducers • Sensitive CYP3A4, CYP2B6, CYP2C8, CYP2C9, CYP2C19, P-gp and Breast Cancer Resistance Protei (BCRP) substrates with a narrow therapeutic window 	None
E	Other		
E1	Study eye not determined	If the study eye is not indicated in the eCRF	None
E2	Missing data	No post-baseline assessment of CSFT	None
E3	Incorrect timing	Assessment of primary endpoint CSFT not within the time window	None

6.3 PATIENT SETS ANALYSED

The statistical analysis will be based on the following populations:

Treated Set (TS)

The TS will consist of all patients who were treated with at least one dose of study drug (BI 1026706 or placebo).

Full Analysis Set (FAS)

The FAS will consist of all patients who were randomised, treated with at least one dose of BI 1026706/placebo and provided baseline and at least one post-randomization CSFT measurement.

Pharmacokinetic Analysis Set (PKS)

[figure not shown]
The PKS will consist of all patients in the TS for whom at least one evaluable BI 1026706 plasma concentration is available.

Table 6.3: 1 Patient sets analysed

Class of endpoint	TS	Patient set	
		FAS	PKS
Primary endpoints		primary analysis	
Further endpoints		X	
Safety endpoints	X		
Pharmacokinetic endpoints			X
Demographic/baseline endpoints	X	(X)	

(X) An additional FAS presentation of the demographic/baseline endpoints may be provided in the EoT section, if patient numbers for FAS and treated set are clearly different (i.e., a non-negligible number of treated patients does not have post randomization data for the primary endpoint).

Note that the number of patients with available data for an endpoint may differ. For details, see section “Handling of missing data”.

6.5 POOLING OF CENTRES

This section is not applicable because centre/country is not included in the statistical model.

6.6 HANDLING OF MISSING DATA AND OUTLIERS

For the primary analysis of the primary endpoint, if a patient misses a visit, the missing data will not be imputed and only on-treatment data will be included. The mixed effect model will handle missing data based on a likelihood method based on the “missing at random”

assumption. Every randomised patient with at least baseline and one on-treatment measurement will be included in the analysis.

To evaluate the impact of any missing data to the analyses of primary endpoint, multiple imputation will be used to handle missing data as a sensitivity analysis. All variables included in the analysis model will be included in the imputation model. In addition, after exploring the missing data mechanism and observed measurements on the blinded data, additional variables may be identified and added to the imputation model.

If the data is monotone missing, a regression model will be used for imputation including baseline CSFT and primary endpoint at Visits 3, 4, 5 by treatment, and stratification factor previous DME treatment.

In the case of non-monotone missing, a Markov chain Monte Carlo (MCMC) step will be used to create monotone missing data in multiple datasets. The regression method will then be used to complete the imputation in each dataset. For each imputed complete dataset, the primary MMRM model described in [Section 7.4](#) will be used for the analyses. The results will be pooled following the standard multiple imputation procedure.

Missing or incomplete AE dates will be imputed according to BI standards (“Handling of missing and incomplete AE dates”) [8]. Missing data and outliers of PK data are handled according to [6].

6.7 BASELINE, TIME WINDOWS AND CALCULATED VISITS

Study day will be calculated relative to the date and time of the first dose of double-masked randomised treatment. The day prior to the start of double-masked randomised treatment will be ‘Day -1’ and the start of double-masked randomised treatment will be ‘Day 1’; therefore ‘Day 0’ will not exist.

For efficacy analyses, baseline is defined as the latest measurement on or before the date of the first randomised treatment administration at Visit 2a. Therefore baseline values are measured at Visit 2a for [REDACTED] and endpoints assessed by SD-OCT (i.e., CSFT, [REDACTED] If Visit 2a measurement is missing, then Visit 1 will be used as baseline. [REDACTED]

[REDACTED] Visit 1 measurement will be used as baseline as per Flow Chart.

Planned time windows are defined in the CTP. For analyses purposes, data from Ophthalmological exams will be allocated to visits by means of windows with the limit between adjacent windows half-way between the planned dates for the visits; the middle day is counted to the window of the later visit. For example, Visit 2a is planned on Day 1 and Visit 2b is planned on Day 8. Therefore, the window of Visit 2a reaches until Day 3, the windows of Visit 2b starts on Day 4. If there are multiple measurement values within one window, 3 cases have to be distinguished:

The following time windows are planned:

- Pre-treatment, the latest measurement is to be selected as baseline as described above;

- After study treatment start, the value closest to the nominal day will be selected for assessment endpoints at a particular visit and for by-visit displays. All values will be stored in analysis datasets;
- For post-treatment, the lastest value in the respective window will be used .

Table 6.7:1 Time windows of treatment period visits

Window No.	Window label	Nominal visit	Nominal day	
-4	Screening	VISIT 1	-28	
0	Baseline	VISIT 2a	1	
1	Week 1	VISIT 2b	8	
4	Week 4	VISIT 3	29	
8	Week 8	VISIT 4	57	
12	Week 12	VISIT 5/EOT ¹	85	
16	Week 16	VISIT 6/EOS	113	

1. Patients may stop study medication prematurely at any visit before Week 12, the nominal day and interval will remain missing in analysis datasets..

These windows will also be used for safety laboratory assessments. If there are multiple measurements within one window, the last value will be used as confirmation.

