### **3.3.4 Removal of patients from therapy or assessments**

#### **3.3.4.1 Removal of individual patients**

An individual patient is to be withdrawn from study treatment if:

- The patient withdraws consent for study treatment or study participation, without the need to justify the decision.
- The patient needs to take concomitant drugs that interfere with the investigational product in the clinical judgement of the Investigator (please refer to [Section 4.2.2](#)).
- The patient can no longer be treated with trial medication for other medical reasons (such as surgery, adverse events, other diseases, or pregnancy).

Patients who drop out prior to randomization will be considered screening failures. They will be recorded as screening failures in the electronic Case Report Form (eCRF) and no further follow-up is required. The data will be included in the trial database and will be reported.

Patients who discontinue or withdraw from the study after randomization (Visit 2a) will be considered as “early discontinuations” and the reason for premature discontinuation must be recorded in the eCRFs. For patients stopping the treatment prematurely before end of week 12, all investigations according to Visit 5/EOT should be done as soon as possible after stopping the study drug. The End of study Visit (Visit 6) will be performed 28 days after Visit 5/EOT in all patients, as outlined in the [Flow Chart](#) and [Section 6.2.3](#). The data will be included in the trial database and will be reported.

Patients who withdraw or discontinue from the trial after randomization will not be replaced.

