#### 5.3.6.2 Adverse event collection and reporting

##### **AE Collection**

The Investigator shall maintain and keep detailed records of all AEs in their patient files. The following must be collected and documented on the appropriate eCRF by the Investigator:

- From signing the informed consent onwards through the Residual Effect Period (REP) until individual patient's end of study:
  - all AEs (serious and non-serious) and all AESIs.
- After the individual patient's end of study:
  - the Investigator does not need to actively monitor the patient for AEs but should only

report SAEs and AESIs of which the Investigator may become aware of, if considered relevant by the Investigator.

[figure not shown]

Figure 5.3.6.2: 1 Collection and reporting of AEs/SAEs during the study

The REP is defined as 4 days after the last trial medication application. All AEs which occurred through the treatment phase and throughout the REP will be considered as on treatment; please see [Section 7.3.4](#). Events which occurred after the REP will be considered as post-treatment events.

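### SAP visit windows run from first dose with no on-drug condition, so the off-drug Visit 6 of early stoppers is labelled Week 4, 8 or 12 in descriptive laboratory and ophthalmology displays

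*SAP*

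**What the plan says.** SAP Section 6.7 fixes the clock: "Study day will be calculated relative to the date and time of the first dose of double-masked randomised treatment". It then states that "data from Ophthalmological exams will be allocated to visits by means of windows with the limit between adjacent windows half-way between the planned dates", and that "the middle day is counted to the window of the later visit". Table 6.7:1 gives nominal days 1, 8, 29, 57, 85 and 113 for Visits 2a, 2b, 3, 4, 5/EOT and 6. The section extends the scheme beyond the eye examinations: "These windows will also be used for safety laboratory assessments".

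Three choices are set out for several values in one window. The one for values after treatment reads "For post-treatment, the lastest value in the respective window will be used". A footnote attached to Visit 5/EOT leaves the nominal day and interval missing for patients who stop early. It does not mention Visit 6.

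Protocol Section 3.3.4.1 has early stoppers attend a premature EOT visit promptly after stopping, and adds that "The End of study Visit (Visit 6) will be performed 28 days after Visit 5/EOT in all patients". The Flow Chart schedules SD-OCT, slit lamp and safety blood tests at Visit 6. Protocol Section 5.3.6.2 sets the residual effect period: "The REP is defined as 4 days after the last trial medication application".

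**The concern.** The windows know how long ago a patient started drug, but not whether the patient is still taking it. Someone who stops early reaches Visit 6 on a study day that belongs to a treatment-period visit of a patient still on drug. The rule then gives the Visit 6 value that visit's label.

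Two things are at stake in the by-visit summaries. First, a Week 8 or Week 12 table would combine values under treatment with values about four weeks after stopping. Protocol Section 3.1 also makes patients eligible for standard of care once they withdraw from study medication, so an ocular value labelled Week 12 could follow other DME treatment. The exclusion of data after rescue is stated only for the primary analysis (SAP Section 7.4). Second, the same readings are missing from the Week 16 summary, where a reader would look for off-drug follow-up. Safety and tolerability are part of the primary objective (Protocol Section 2.2), so these tables will be read.

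**Working it through.** **Inputs.** Nominal days 1, 8, 29, 57, 85, 113; limit half-way between adjacent days; middle day to the later visit (all SAP Section 6.7). Visit 6 = EOT visit + 28 days (Protocol Sections 3.3.4.1 and 6.2.3).

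**1. Reproduce the SAP's own example.** The midpoint of Visits 2a and 2b is (1 + 8)/2 = 4.5. The SAP says that "the window of Visit 2a reaches until Day 3, the windows of Visit 2b starts on Day 4", so a half-day midpoint is rounded down.

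**2. Window starts.**
- Week 4: (8 + 29)/2 = 18.5, so Day 18
- Week 8: (29 + 57)/2 = 43
- Week 12: (57 + 85)/2 = 71
- Week 16: (85 + 113)/2 = 99

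Hence Week 4 = Days 18-42, Week 8 = Days 43-70, Week 12 = Days 71-98, and Week 16 runs from Day 99. The last three limits are whole numbers, so rounding does not affect them.

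**3. Where Visit 6 lands (EOT day + 28).**

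| EOT day | Window of EOT | Visit 6 day | Window of Visit 6 |
|---|---|---|---|
| 2-3 | Baseline | 30-31 | Week 4 |
| 4-14 | Week 1 | 32-42 | Week 4 |
| 15-17 | Week 1 | 43-45 | Week 8 |
| 18-42 | Week 4 | 46-70 | Week 8 |
| 43-70 | Week 8 | 71-98 | Week 12 |
| 71-90 | Week 12 | 99-118 | Week 16 |

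Only an EOT visit on Day 71 or later gives Visit 6 its intended label. In every row Visit 6 falls in a later window than the EOT value. So the EOT value is not displaced, and the rules for choosing among values in one window do not remove the Visit 6 value.

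**4. Sensitivity to the interval.** No tolerance for Visit 6 is readable. If the interval were 25 days (assumption), the EOT days leading to Week 8 or 12 would be 43 - 25 = 18 to 98 - 25 = 73. At 31 days they would be 43 - 31 = 12 to 98 - 31 = 67.

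**5. Time off drug.** About 28 days, against a residual effect period of 4 days: 28/4 = 7 times as long.

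**6. Number of patients.** The documents give no dropout rate. As an assumption, if 5%, 10% or 20% of 50 patients per arm have EOT on Days 15-70 and attend Visit 6, that is 2.5, 5 or 10 per arm.

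**7. Which outputs are exposed.**
- Primary CSFT model: SAP Section 6.6 admits only on-treatment data, and SAP Section 6.1 classes everything from the day after the last dose as post-treatment. Visit 6 values do not enter.
- Adverse events: timed by last dose plus 4 days (SAP Sections 6.1 and 7.8.1), not by these windows.
- Laboratory tables: SAP Section 7.8.2 plans descriptive statistics with no on-treatment condition. Exposed.
- Ophthalmology: SAP Section 6.7 refers to by-visit displays, also with no such condition. Exposed to the extent that these are produced.

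**The case against.** The strongest reply is that the SAP already knows these values are off drug. Section 6.1 defines periods from actual start and stop dates, and Section 6.7 itself distinguishes values after treatment. A reader might infer that Visit 6 readings would be analysed as treatment-period data or reach the primary comparison. The documents do not support that: the values keep post-treatment status, and the primary model excludes them. The affected outputs are descriptive, with no hypothesis test planned for safety.

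A reader might also infer that a safety signal would be diluted or lost. That is not shown. The EOT value stays in its own window, clinically relevant findings are recorded as adverse events, individual values are listed by visit (SAP Section 7.8), and the second laboratory output counts patients with possible clinically significant abnormalities, which a later normal value need not cancel. Nothing in the documents says that patients who stop have recovered by Visit 6. Tonometry is not scheduled there. Completers still populate Week 16.

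Finally, part of the answer may lie in text that cannot be seen: the interval column of Table 6.7:1 is blank as extracted, further-endpoint sections are redacted, and laboratory handling follows a company standard that is not supplied.

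All of this limits the consequence. It does not remove the mislabelling. The post-treatment rule chooses among values within a window and moves none out. The footnote is attached to Visit 5/EOT. If it leaves the premature EOT value without a window, the reading nearest to exposure loses its label while the off-drug one gains one.

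**Conclusion.** The point stands in a limited form and is worth correcting. As written, SAP Section 6.7 gives the off-drug Visit 6 of an early stopper a Week 8 label (EOT Days 15-42), a Week 12 label (EOT Days 43-70), or a Week 4 label (EOT on about Day 14 or earlier). The consequence is confined to by-visit laboratory summaries and any by-visit ophthalmology displays, where values about 28 days off drug would sit among on-drug values and be absent from Week 16. The primary CSFT analysis and the adverse event tables are not affected.

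The day ranges assume an interval of exactly 28 days and that the footnote does not reach Visit 6. The number of patients is unknown; the per-arm counts above are illustrations. The direction of any bias is plausible but not demonstrated.

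**What to change.** In SAP Section 6.7 and Table 6.7:1, allocate Visit 6 and any other assessment after the EOT visit to a follow-up window timed from EOT (nominal EOT + 28 days), and not to the Week 1-12 windows. Apply this to both ophthalmology and laboratory displays. Keep the EOT assessment in its day-based window, flagged if it falls more than 4 days after the last dose, and reword the footnote to agree.

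The cost is SAP wording and one derivation from the dosing and visit dates. The downside is slightly fewer patients in the Week 4, 8 and 12 tables.
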